7.4 Derived Data

Age

- Age (in years) = INT{(Operative Date)-(Date of Birth)+ 1/365.25}

Body Mass Index (BMI)

- BMI = {(Weight in kg)/(Height in m)²}, if units are in kg for weight and m for height OR;
- BMI = {(Weight in lbs)x703.07})/(Height in inches)²}, if units are in lbs for weight and inches for height (Adjustments made to formula to standardize BMI unit to kg/m²)

Time to Revision

- Time to revision (in months) = (Revision Date – Operative Date + 1)/30.4375

CONFIDENTIAL AND PROPRIETARY

This document contains information that is confidential and proprietary to Smith & Nephew PLC and Smith & Nephew, Inc. and is intended for use only by Smith+Nephew and its manufacturer. It shall not be reproduced or copied in whole or in part, nor shall the contents be disclosed by any means without prior written permission from Smith+Nephew, nor shall anyone make any use of it that is contrary to the expressed or implied wishes of Smith+Nephew.

Statistical Analysis Plan

A Prospective, Multi-Center, Non-Randomized, Safety and Efficacy Clinical Study of the LEGION™ Primary Knee System for Primary Total Knee Replacement in Subjects with Degenerative Knee Disease

Number: 10-4042
ST: 1113
Version: Final 1.0, 15-Feb-2021
Page: 10 of 18

Change from pre-operative to post-operative visits

Change from pre- to post-operative visit would be calculated as:

$$\text{Post - operative value}_{\text{visit } n} - \text{Pre - operative value}_{(\text{visit } 1)}, \text{ where } n = 3, 4, \dots$$

Knee Society Score (KSS) Endpoints

The Knee Society Score (KSS) comprises information on Objective Knee Indicators (range 0 to over 100 points), Patient Satisfaction (range 0-40), Patient Expectation (range 0-15), and Functional Activities (range 0-100). The KSS endpoints are derived from a series of questions that relate to everyday activities. More elaborate information for deriving the KSS endpoints are described in the publication by Scuderi et al (2012). However, an abbreviated description of the KSS endpoints used in the study is described in this SAP.

- *Objective Knee Score (Completed by Physician/Surgeon)*
- The objective score allows for more than 100 points in patients with greater than 125° of flexion and a stable painless knee as outlined below.
 - “Alignment” allows for a maximum of 25 points and is determined on a weight-bearing AP radiograph measuring the femoral-tibial (Anatomic) axis.
 - “Instability” allows for a maximum of 25 points for a knee that is stable in the coronal and sagittal axis.
 - “Joint Motion” allows one point for each 5° of joint motion with a potential for greater than 25 points to be assigned for patients with greater than 125° of motion. There are deductions for flexion contracture and extension lag.
 - “Instability” has a maximum allowable point allocation of 25+.
 - “Symptoms” category contains two 10-level scales, ranging from “none” to “severe” for each patient to rate pain encountered when walking on level ground and on stairs/inclines. For this, a patient starts with 10 points on each scale for a painless knee with deductions of up to 10 points deductions as indicated by the patient’s

CONFIDENTIAL AND PROPRIETARY

This document contains information that is confidential and proprietary to Smith & Nephew PLC and Smith & Nephew, Inc. and is intended for use only by Smith+Nephew and its manufacturer. It shall not be reproduced or copied in whole or in part, nor shall the contents be disclosed by any means without prior written permission from Smith+Nephew, nor shall anyone make any use of it that is contrary to the expressed or implied wishes of Smith+Nephew.

Statistical Analysis Plan

A Prospective, Multi-Center, Non-Randomized, Safety and Efficacy Clinical Study of the LEGION™ Primary Knee System for Primary Total Knee Replacement in Subjects with Degenerative Knee Disease

Number: 10-4042
ST: 1113
Version: Final 1.0, 15-Feb-2021
Page: 11 of 18

response on each pain scale. There is an additional question regarding how "normal" the knee feels to the patient. The maximum allowable point is 25.

Patient Expectations and Satisfaction (Completed by Patient)

- "Patient Expectations" is a three-question fifteen-point scale that is collected pre-operatively and post-operatively. The pre-operative questions reflect a patient's opinion on the extent to which s/he expects that the operation will improve his/her knee pain, and the ability to perform activities of daily living and recreational activities.
- The post-operative patient expectations questions reflect the extent to which the outcome after the operation has met the patient's pre-operative expectations with respect to pain and function. "Patient Satisfaction" is a five-question 40-point scale that is collected preoperatively and at each follow-up visit.
- *Functional Score (Completed by Patient)*

CONFIDENTIAL AND PROPRIETARY

This document contains information that is confidential and proprietary to Smith & Nephew PLC and Smith & Nephew, Inc. and is intended for use only by Smith+Nephew and its manufacturer. It shall not be reproduced or copied in whole or in part, nor shall the contents be disclosed by any means without prior written permission from Smith+Nephew, nor shall anyone make any use of it that is contrary to the expressed or implied wishes of Smith+Nephew.

Statistical Analysis Plan

A Prospective, Multi-Center, Non-Randomized, Safety and Efficacy Clinical Study of the LEGION™ Primary Knee System for Primary Total Knee Replacement in Subjects with Degenerative Knee Disease

Number: 10-4042
ST: 1113
Version: Final 1.0, 15-Feb-2021
Page: 12 of 18

- The functional score is composed of the four subgroups and has a maximum score of 100 as follows:
 - “Walking and Standing” has a maximum value of 30 points with deductions for the use of walking aids and supports.
 - “Standard Activities” has a maximum of 30 points and evaluates “standard” activities of daily living. Patients can also respond if they never participate in the activities. Patients who respond “I never do this” receive zero points for that activity.
 - “Advanced Activities” has a maximum of 25 points and evaluates function in performing more vigorous activities ranging from climbing a ladder or step-stool to running. Patients can also respond if they never participate in the activities. Patients who respond “I never do this” receive zero points for that activity.
 - “Discretionary Activities” has a maximum of 15 points and allows patients to select the three activities that they consider most important to them personally from a group of seventeen recreational and exercise activities. Patients who do not participate in any of the discretionary activities will have a functional knee score that is limited to 85 points. The discretionary activities do not need to be identical in the pre-operative and post-operative period.

Knee Osteoarthritis Outcome Score (KOOS)

Each item (question) that is used for scoring the KOOS is rated on a scale of 0 to 4 as follows:

- 0 = None; 1 = Mild; 2 = Moderate; 3 = Severe and; 4 = Extreme.

CONFIDENTIAL AND PROPRIETARY

This document contains information that is confidential and proprietary to Smith & Nephew PLC and Smith & Nephew, Inc. and is intended for use only by Smith+Nephew and its manufacturer. It shall not be reproduced or copied in whole or in part, nor shall the contents be disclosed by any means without prior written permission from Smith+Nephew, nor shall anyone make any use of it that is contrary to the expressed or implied wishes of Smith+Nephew.

Statistical Analysis Plan

A Prospective, Multi-Center, Non-Randomized, Safety and Efficacy Clinical Study of the LEGION™ Primary Knee System for Primary Total Knee Replacement in Subjects with Degenerative Knee Disease

Number: 10-4042
ST: 1113
Version: Final 1.0, 15-Feb-2021
Page: 13 of 18

A minimum of 50% of all items for each subscale of the KOOS will be responded to before a subscale score is derived. Table 2 thus indicates for each subscale, the minimum number of items to be scored for a KOOS subscale endpoint to be calculated.

Table 2. Minimum number of items required and algorithms for a KOOS subscale score.

Subdomain	Minimum number of Items needed for calculation of subdomain score	Algorithms for subdomain scoring
Pain (P1 – P9)	5	$100 - \frac{\text{Mean Score (P1 – P9)} \times 100}{4}$
Symptoms and Stiffness (S1 – S7)	4	$100 - \frac{\text{Mean Score (S1 – S7)} \times 100}{4}$
Function, daily living (A1 – A17)	9	$100 - \frac{\text{Mean Score (A1 – A17)} \times 100}{4}$
Sports and recreational activities (SP1 – SP5)	3	$100 - \frac{\text{Mean Score (SP1 – SP5)} \times 100}{4}$
Quality of Life (QoL) (Q1 – Q4)	2	$100 - \frac{\text{Mean Score (Q1 – Q4)} \times 100}{4}$

Each subscale is scored independently at each visit. The mean score of the individual items of each subscale are calculated and divided by 4. A score of 100 indicates that by that visit the subject has no problems while a score of 0 is indicative of severe problems on each of the subscale scores.

7.5 Baseline Data

The following demographic and baseline variables whose information is available either at the preoperative or the operative visits will be summarized using descriptive characteristics for continuous¹ or categorical² data as follows:

CONFIDENTIAL AND PROPRIETARY

This document contains information that is confidential and proprietary to Smith & Nephew PLC and Smith & Nephew, Inc. and is intended for use only by Smith+Nephew and its manufacturer. It shall not be reproduced or copied in whole or in part, nor shall the contents be disclosed by any means without prior written permission from Smith+Nephew, nor shall anyone make any use of it that is contrary to the expressed or implied wishes of Smith+Nephew.

Statistical Analysis Plan

A Prospective, Multi-Center, Non-Randomized, Safety and Efficacy Clinical Study of the LEGION™ Primary Knee System for Primary Total Knee Replacement in Subjects with Degenerative Knee Disease

Number: 10-4042
ST: 1113
Version: Final 1.0, 15-Feb-2021
Page: 14 of 18

- Age¹ (in years),
- Sex² (males or females),
- Bilateral Status² (unilateral or bilateral),
- Body Mass Index (BMI)¹

Age will additionally be categorically summarized into \leq 60 years versus >60 years while BMI will further be summarized into $\leq 30 \text{ kg/m}^2$ versus $>30 \text{ kg/m}^2$.

7.6 Disposition Data

The disposition of subjects (knees) will be summarized as using accountability of clinical follow-up of the subjects' knee from the preoperative, operative through the 10 year postoperative follow-up. Information that will be summarized in this table will include but not only restricted to theoretically due, revisions, terminations, expected knees at visit, not yet overdue at visit and knees evaluated at visit.

7.7 Protocol Deviations

A listing of cumulative protocol deviations encountered on-study will be presented for each subject (and/or knee) with deviations.

7.8 Measurement of Treatment Compliance

Not applicable.

7.9 Multiplicity

Not applicable.

CONFIDENTIAL AND PROPRIETARY

This document contains information that is confidential and proprietary to Smith & Nephew PLC and Smith & Nephew, Inc. and is intended for use only by Smith+Nephew and its manufacturer. It shall not be reproduced or copied in whole or in part, nor shall the contents be disclosed by any means without prior written permission from Smith+Nephew, nor shall anyone make any use of it that is contrary to the expressed or implied wishes of Smith+Nephew.

Statistical Analysis Plan

A Prospective, Multi-Center, Non-Randomized, Safety and Efficacy Clinical Study of the LEGION™ Primary Knee System for Primary Total Knee Replacement in Subjects with Degenerative Knee Disease

Number: 10-4042
ST: 1113
Version: Final 1.0, 15-Feb-2021
Page: 15 of 18

7.10 Analysis of Primary Endpoint

- Kaplan-Meier product limit survival estimates will be used to estimate implant (device) survivorship, $S(t)$ where $S(t)$ is the proportion of knees without an implant revision at time t . Time to implant revision is the endpoint of interest in the determination of implant survivorship. The cumulative proportion of knees with implant survivorship at 3 months, 12 months (1 year), 24 months (2 years), 36 months (3 years), 60 months (5 years), 84 months (7 years) and 120 months (10 years) will be estimated and displayed accordingly. Knees that are still on-study without a revision will be censored on that date of database lock. A prematurely discontinued knee from study as a result of death or for any other reason will be censored on the discontinuation date. A subject lost to follow-up prior to the database lock will have the contributory knee censored on the last known contact date. Kaplan-Meier estimates for implant survivorship will be presented with the corresponding two-sided 95% Confidence Intervals (CIs). Kaplan-Meier survival graphs will also be displayed.
- A listing of subjects with revised implants and the components revised would be provided.
- The Kaplan-Meier product limit estimates will further be presented after stratifying by age group, BMI group and gender.

CONFIDENTIAL AND PROPRIETARY

This document contains information that is confidential and proprietary to Smith & Nephew PLC and Smith & Nephew, Inc. and is intended for use only by Smith+Nephew and its manufacturer. It shall not be reproduced or copied in whole or in part, nor shall the contents be disclosed by any means without prior written permission from Smith+Nephew, nor shall anyone make any use of it that is contrary to the expressed or implied wishes of Smith+Nephew.

Statistical Analysis Plan

A Prospective, Multi-Center, Non-Randomized, Safety and Efficacy Clinical Study of the LEGION™ Primary Knee System for Primary Total Knee Replacement in Subjects with Degenerative Knee Disease

Number: 10-4042
ST: 1113
Version: Final 1.0, 15-Feb-2021
Page: 16 of 18

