- Any device component experiencing dislocation, subluxation, subsidence, or migration.

All serious adverse events, life-threatening problems, or deaths that occur during or following the use of the devices during the study should be fully documented in the research record by the Investigator including the onset date, complete description of the event, severity, duration, action taken, and outcome. The event should be documented on the appropriate interval and case report form. The investigator will be responsible for notifying the reviewing ethics committee or IRB of any unanticipated adverse events. The Investigator will record all non-serious, device-related adverse events on the appropriate case report form. All adverse events must be followed until they resolve, or are considered final.

Adverse events that are serious, unanticipated and possibly device-related must be reported in detail by the Investigator to Smith & Nephew and the reviewing IRB as soon as possible, but in no event later than ten working days after the Investigator first learns of the event.

H. End of Study

Study completion status of the subject (e.g. completed per protocol, subject withdrawal, device removed, death, lost-to-follow-up, or other reason) is to be recorded. A subject having a specified objection to continuing in the study will be withdrawn. Any subject who withdraws from the study postoperatively will be considered in the data analysis up until the time of their withdrawal. Subjects lost to follow-up will be documented on the End of Study form. All reasonable efforts should be made to keep in contact with the subject for the 10 year duration of this study.

Subjects may be taken out of the study without their consent for the following reasons:

- ✓ The Investigator decides that continuing the study would be harmful
- ✓ Participants miss so many appointments that their data cannot be used in the study
- ✓ The study Sponsor (Smith & Nephew, Inc.) decides to end the study

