The cumulative percent survival for the study device is unknown for this population, but there is no reason to believe that it would be less than the reference rate. Therefore, a conservative success rate of 93.1% for the study device is used at 10 years. The non-inferiority margin δ of 0.07 is chosen in the study (p13, Chow, Shao, and Wang, 2003). 96 subjects are required to achieve $100(1 - \beta)\% = 80\%$ power to detect non-inferiority at the Significance level of $\alpha = 0.05$. Based on the experience study, allowing 30% of the subjects lost to follow up by the end of 10 years, a sample size of at least 138 subjects are needed in this study. Therefore, a total of 138 subjects will be enrolled into the study in up to 8 clinical sites.

C. Statistical Methods

Primary and secondary outcomes will be evaluated with the use of listings and summary statistics. 95% confidence intervals will be calculated for proportions and averages corresponding to the clinically significant outcomes. Improvement in pain and function will be analyzed using t-test or Wilcoxon Rank tests. Kaplan-Meier estimates will be used to analyze the survivorship of the prosthesis. For survivorship analyses, revision will be defined as failure. Adjustment of prognostic factors to the improvement in outcomes will be performed if needed using appropriate parametric or non-parametric statistical analysis. All statistical analyses and calculation of confidence intervals will be performed using SAS or other appropriate statistical software. An alpha value of $\alpha=0.05$ will be used in all hypothesis testing.

Experience from numerous studies has revealed that most of the missing data are usually due to lost to follow-up, revision, death and subject withdrawal. A complete accountability along with the explanation for lost-to-follow-up, death, revision, and withdrawn subjects will be provided in the final study report. The missing due to revision will be treated as device failure. A complete assessment of the informative/non-informative missing data will be performed using Kaplan-Meier (KM) method. The KM estimate of the success rate along with the 95% confidence interval of the estimate will be included in the final report.

IX. STUDY SUPERVISION

A. Investigator Responsibilities

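### SAP 7.10 describes S(t) as the proportion of knees without a revision but censors deaths, so 1 − S(t) is a net risk that somewhat overstates the proportion of knees actually revised

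*SAP*

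**What the plan says.** SAP 7.10 uses Kaplan-Meier for the primary endpoint, cumulative percent survival, and defines S(t) in words: it "is the proportion of knees without an implant revision at time t". On exits it says: "A prematurely discontinued knee from study as a result of death or for any other reason will be censored on the discontinuation date". Subjects lost to follow-up are handled separately and censored at last known contact. Estimates start at 3 months, and those at "84 months (7 years) and 120 months (10 years) will be estimated and displayed accordingly". The curves are repeated after "stratifying by age group, BMI group and gender"; SAP 7.5 sets the age groups at 60 or below and above 60.

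Protocol VIII.C says: "For survivorship analyses, revision will be defined as failure". It also expects deaths, stating that "most of the missing data are usually due to lost to follow-up, revision, death and subject withdrawal", and proposes to assess informative and non-informative missingness by Kaplan-Meier. Protocol VI.H makes death one of the exit statuses that the site records.

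SAP 7.15 drops the non-inferiority test because the study is ending early, and leaves the primary endpoint descriptive. Neither document plans a cumulative incidence of revision, or says that the reported survivorship is conditional on no deaths. Neither gives a mortality rate or an age-specific revision rate.

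**The concern.** The verbal definition and the estimator describe different quantities. A knee whose owner has died unrevised can no longer be revised. Censoring it lets the knees still under follow-up stand in for it, as though it remained at risk. The result is net survivorship, that is, revision risk with death removed. The proportion of implanted knees that reach revision in a population where people also die is the cumulative incidence, and it is lower.

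With the test gone, the reported number and its label are the whole primary result. A reader who takes the label literally will read 1 − S(t) as the share of knees revised. In the age-stratified display, if mortality differs between the groups, the curves compare net revision risk and not the proportions revised.

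A second, smaller gap is that the SAP does not say what the discontinuation date is for a subject who dies. If it is later than the death, the knee stays in the risk set when it can no longer fail.

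**Working it through.** **Inputs.** Planning value for device survival at 10 years: 93.1% (Protocol VIII.B, SAP 6.1). Reference at 10 years: about 93.7% (Protocol VIII.B). Planned enrolment: 138, with 96 evaluable. Ten-year mortality p is not in the documents; 5% to 30% is assumed. Revision and death are taken as independent with constant hazards, and other censoring as non-informative.

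**The plan's own figure.** From 95.0% at 8 years, λ = −ln(0.95)/8 = 0.0064 per year, as Protocol VIII.A states. Then exp(−10 × 0.0064) = 0.938, against the stated approximate 93.7%. The constant-hazard form used below is therefore the plan's own.

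**Formulas.** Revision hazard r = −ln(0.931)/10 = 0.00715 per year. Death hazard d = −ln(1 − p)/10. Complement of Kaplan-Meier with deaths censored: 1 − exp(−rt). Cumulative incidence of revision: r/(r + d) × [1 − exp(−(r + d)t)].

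Example at p = 20%: d = 0.0223 and r/(r + d) = 0.243. Also exp(−10(r + d)) = 0.931 × 0.80 = 0.745, so the cumulative incidence is 0.243 × 0.255 = 0.062.

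| Deaths by 10 years (assumed) | 1 − KM | Cumulative incidence | Gap, points | Ratio |
|---|---|---|---|---|
| 5% | 6.90% | 6.73% | 0.17 | 1.03 |
| 10% | 6.90% | 6.55% | 0.35 | 1.05 |
| 15% | 6.90% | 6.37% | 0.53 | 1.08 |
| 20% | 6.90% | 6.19% | 0.71 | 1.11 |
| 30% | 6.90% | 5.82% | 1.08 | 1.19 |

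Starting from 93.7% gives the same ratios. A simulation of 400,000 knees at 93.7% and 20% deaths gave 6.34% for 1 − KM against 5.69% actually revised.

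**Earlier time points.** At 93.1%, the gap is 0.14 points at 5 years and 0.27 at 7 years with 15% ten-year mortality, and 0.29 and 0.56 with 30%.

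**Scale.** With one knee per subject and no censoring, the 95% half-width is 1.96 × √(0.931 × 0.069/138) = 4.2 points. In 138 knees, 30% mortality means 138 × 0.069 = 9.5 implied revisions against 138 × 0.0582 = 8.0.

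**Age strata.** Both the revision and the death rates below are assumed.

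| Case | Group | Net revision | Deaths | Gap, points | Ratio |
|---|---|---|---|---|---|
| Equal revision risk | ≤60 | 6.3% | 5% | 0.16 | 1.03 |
| | >60 | 6.3% | 25% | 0.82 | 1.15 |
| Higher risk in younger | ≤60 | 12% | 8% | 0.48 | 1.04 |
| | >60 | 3% | 25% | 0.39 | 1.15 |

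The order in percentage points reverses between the two cases. The order in ratio does not.

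**Date of exit.** If each death were dated at the next scheduled visit (mean lag about 1 year), simulated 10-year Kaplan-Meier survival rises from 0.9305 to 0.9315 with 15% deaths, and from 0.9308 to 0.9331 with 30%. That is 0.1 to 0.2 points, in the direction of too few revisions.

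**The case against.** The strongest defence is that net survivorship is a coherent target for an implant, and that the SAP is open about it. It names implant survivorship as the quantity, time to revision as the endpoint, and death as a reason for censoring. On this reading the phrase about proportions is loose wording and not a promise of a crude proportion. One minus the cumulative incidence also has a drawback, because it counts every unrevised knee of a deceased subject as a success and so rises with mortality. These points stand, and they are why Kaplan-Meier should stay. They do not make the label correct.

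It is also fair that the effect is small, that it overstates revision and so does not flatter the device, and that no test depends on it. The 19% figure needs 30% deaths, which would use up the plan's whole 10-year attrition allowance if deaths are counted within it. Because the study is ending early, 10-year data may be sparse, and the gap is smaller at the earlier time points.

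Three stronger readings are tempting, but the documents do not support them:

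- **The older group is distorted most.** This holds for the ratio if mortality is higher above 60. In percentage points it also depends on each group's revision risk, which is not given.
- **Deaths will be dated late.** The exit date for a death is simply undefined. Protocol VI.G asks for the onset date when a death is documented, the exit form is completed as needed and not only at visits, and Protocol XI.D has sites find out whether non-respondents have died.
- **Kaplan-Meier must be kept because it matches the registry reference.** Protocol VIII.A does not say how the registry handled deaths.

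**Conclusion.** The point holds as a mismatch between label and estimator. As planned, S(t) is death-censored implant survivorship, and its complement overstates the proportion of knees revised whenever deaths occur. Over assumed 10-year mortality of 5% to 30%, with constant independent hazards and 93.1% net survival, the overstatement at 10 years is about 0.2 to 1.1 points, or 3% to 19% relative. The size rests on those assumptions; the direction needs only that some subjects die while their knee could still have been revised.

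The age-stratified curves compare net risk. Which group is more affected in percentage points cannot be determined from the documents. The undefined exit date is a minor gap that would act in the opposite direction.

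None of this makes Kaplan-Meier a wrong choice or threatens a conclusion about the device. It is a cheap improvement, worth making because the descriptive figure is now the primary result.

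**What to change.** In SAP 7.10:

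- Keep Kaplan-Meier as the primary summary, and describe S(t) as implant survivorship with death censored.
- Add the Aalen-Johansen cumulative incidence of revision with death as a competing event, with 95% confidence interval and number of deaths, at the same time points, overall and by age group. The BMI and gender strata can be left out: about 9.5 expected revisions before attrition will not support much splitting.
- State that for a subject who dies the exit time in both analyses is the date of death.

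The cost is a few lines of SAP text and one more standard procedure on data that the study already collects, since death is a recorded exit status and deaths are to be documented with their onset date. The downside is two figures in the report that readers must tell apart, so each table and graph should say which quantity it shows.
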